Theoretical Constructs (potential mediators) Self-efficacy: ⁶⁸ domain specific; we will measure confidence for increasing LPA and decreasing SB with 3 items. Social Support for Physical Activity Survey: 4 items using a 5-point scale to measure support from family and friends while making changes to physical activity. Multidimensional Outcome Expectations for Exercise Scale: 15 items to assess physical, social, and self-evaluative beliefs about consequences of being physically active. (Good internal consistency: alpha=0.76-0.84; and Good model fit: RMSEA: ≤0.07; CFI:≥0.92 in older adults) ^{69,70} Behavioral Regulations in Exercise Questionnaire (BREQ-2): 19 items to assess autonomous motivation on a continuum from amotivation to intrinsic motivation. Will be adapted using identical anchors for LPA. (Good internal consistency: alpha=0.74-0.91; excellent model fit: RMSEA=0.02; CFI=0.95) ^{71,SP-72} Perceived Autonomy Support – Sport Climate Questionnaire (short form): 6 items to assess autonomy support of the health coach to characterize the quality of the social environment for influencing motivation.	X	X	X
	X	X	X
	X	X	X
	X	X	X

****NOTE:** Additional data will be provided by the NMTR to characterize the non-responders. NMTR will provide the aggregate status (total count) based on their attempt to contact the patient, prior to releasing names to study staff. The status values include:

- Released, Patient actively or passively agreed to participant in this study
- Refused, Patient actively refused to participate in this study
- Do Not Contact, patient is eligible to participate but does not want to be contacted for any studies
- Bad Address, unable to contact the patient because the letter was undeliverable
- Ineligible, the patient was ineligible to participate in this study because of age, date of diagnosis, site, etc. This could happen if the patient notifies the NMTR of a discrepancy in their data. I.e. Date of birth is wrong or different diagnosis.
- Deceased, patient died prior to our attempt to contact them or prior to releasing the data to the study.

Additionally, for those patients referred to the study, additional aggregate data (means and standard deviations or total count) will be provided for non-responders (separately by 3 groups: ineligibles, passive refusal, active refusal): cancer site, stage of diagnosis, age and year of diagnosis, and summary treatment.

PROTOCOL TITLE: Whole-of-Day Approach to Physical Activity in Older Cancer Survivors

This intervention trial includes a 3 month follow-up assessment to evaluate whether the behavior change has been maintained (light-intensity physical activity, reduced sedentary activity), and whether the patient-reported outcomes have changed (e.g., quality of life, physical function and physical performance).

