The physical performance tests include the 30-second chair stand test and the 4-stage balance test (see **Table 2**). These tests incorporate movements typically undertaken during normal daily activities, and thus represent tests that are more likely to be safely performed in the home, under supervision of a family member or friend (and remote supervision by the study investigator). Both tests are timed. The first test is the 4-stage balance test and includes four different positions, which the participant will be asked to hold for 10 seconds. The participant may decline to try any of the positions if they feel it is unsafe. Also, if the participant is unable to maintain their balance for 10 seconds, they do not proceed to the next position. The four positions include: feet side-by-side, semi-tandem (one foot slightly behind the other), full-tandem (one foot directly behind the other), standing on one foot; For the 30-second chair stand test, the participant will stand up from a chair without using their arms and sit back down again, and to repeat this for 30 seconds. The participant is instructed to perform the test quickly, but safely, and can slow down or stop before the end of the test. A friend or family member much be present for this portion of the study.

PROTOCOL TITLE: Whole-of-Day Approach to Physical Activity in Older Cancer Survivors

These video calls will be recorded for quality control. These video recordings will be destroyed 3 years after the study closes. The participant is provided with both written and video instructions of how to perform these tests safely, and how to prepare for the videoconference session with the study investigator.

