Once the study team connects a Fitbit account to Fitabase, Fitabase collects all new data that is collected by the device. When the device syncs (i.e., transfers data), Fitabase is notified of data availability, requests the new data, and then processes the data in order to make it available to the study. The study team will download study participant's de-identified data from Fitabase. Fitabase does not collect personally identifiable data. Each study participant is de-identified with a participant ID. Fitabase does not receive the associated email address, the Fitbit account name, Fitbit Friends list, or any GPS data.

Participants will be given Fitabase's Terms of Use and the Privacy Policy upon request. By consenting to use the Fitbit device as part of this study, the participant also consents to the Fitabase Terms of Use and Privacy Policy. At the end of the study, the participant gets to keep the Fitbit device and will receive instructions how to change the email address associated with the Fitbit account. At the end of the study or if a participant withdraws from the study we will disassociate the Fitbit account from the Fitabase account.

Health Coach Calls / MI: Research assistants will undergo MI training specific to this study. MI techniques and micro-skills will be used to guide five sessions of telephone-based health coaching, which will occur during weeks 3, 5, 7, 9, and 11. Key intervention topics and techniques include: establishing rapport; eliciting knowledge about adverse effects of inactivity/SB and benefits to becoming more active; assessing motivation, confidence, perceived importance and barriers to becoming more active; eliciting change talk; and enhancing participants' self-efficacy (competence) and motivation to be more active (e.g., small, achievable goals). The health coach also provides tech support to the participant for assessments (activPAL and performance testing) and using Fitbit with their mobile app (weeks 1, 2, 13, & 26). The first call (week 2) to help the participant set up their Fitbit may take up to 45 minutes, but can be much shorter depending on the participant's comfort level with technology. The first health coaching call may take up to 45 minutes (week 3); the remaining four health coaching calls will take 20 minutes each (weeks 5, 7, 9 and 11). Health coaching calls will be audio recorded and reviewed for quality control. Audio files will be destroyed 3 years after the study closes.

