Follow-up assessment: The ActivPAL3™ monitor, and instructions will be mailed to all participants to collect 1-week of data for secondary outcomes during week 13. The packet will also include questionnaires to assess subjective outcomes (see **Table 2**). The RA will call to review the instructions and answer any questions. The same procedure will be used for the 3-month post-intervention follow-up assessment.

Participant Advisory Board (PAB): The PAB will include 4-5 cancer survivors from the community. The PAB will meet twice per year (years 2-5) with the study team to provide advice and guidance on the protocol and study materials for both the validation study and RCT, interpretation of the study/RCT results, and identify next steps and strategies for the future, larger RCT (R01 application).

Study Flow: The table below describes the flow of the study from recruitment through intervention delivery to assessment of outcomes. Form of contact (phone, email, or mail) is indicated. Important information is conveyed over the phone (e.g., eligibility assessment, consent) and the use of email is dependent on participant preference for minor communication (e.g, reminders).

Fees/ Postage	Phone		Email		Mail	
	IN	OUT	IN	OUT	IN	OUT
\$					X	NMTR-> mail letter about study & flyer
	(X)		(X)		(X)	(Possible reply by potential ppts)

PROTOCOL TITLE: Whole-of-Day Approach to Physical Activity in Older Cancer Survivors

Fees/ Postage	Phone		Email		Mail		
	IN	OUT	IN	OUT	IN	OUT	
							NMTR releases contact info to Study Team
\$					X		Mail letter of invitation, flyer, & consent form
		X		X		X	Recruitment materials to community settings
	(X)		(X)		(X)		Possible reply by potential ppts
		X					Investigator determines interest & eligibility using REDCap recruitment screener 
 • If refusal → Refusal Qs • If interested & eligible → Go to ppt info
		X					Schedule time to review consent w/ ppt
\$				(X)		(X)	Mail or email consent form (if lost copy)
		X					Review consent
\$			X		X		Ppt mails signed consent form or e-signs
						X	Mail ppt photocopy of signed consent form ¹
		X					Once received, investigator contacts ppt to schedule BASELINE assessment, preference for surveys ² (see Assessment Call 1 Script ...)
							Verify receipt of packet and schedule remote assessment w/ [name] via MYHealth calendar (see Assessment Call 2 Script ...)
\$				(X)		X	Survey packet & cover letter mailed to ppt (optional: email w/ REDCap link)

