		X		X			Reminder to ppt about assessment (need another person present for physical function tests) (see Assessment Call 3 Script ...)
		X					Reminder to ppt about assessment (text from [name] with link to Zoom or Skype videoconference session for physical function tests)
		X					Remote assessment conducted / completed via Skype or Zoom
		X		X			Follow-up for incomplete surveys; return of activPAL (see Assessment Call 4 Script ...)
\$						X	Randomization and mail gift card: 
 • Group A: mail thank you (on card stock) and gift card; start intervention; mail cover letter, Fitbit, Fitbit instructions, & MI Visual Aids (1st 2 Health Coaching calls)

PROTOCOL TITLE: Whole-of-Day Approach to Physical Activity in Older Cancer Survivors

Fees/ Postage	Phone		Email		Mail		
 Group B: mail thank you letter (maintain usual activity for 12 weeks; then receive full intervention) and gift card.
	IN	OUT	IN	OUT	IN	OUT	
							Fitbit setup; verify receipt, ask if ppt would like help; reminder: maintain usual activity for 1 week; schedule 1 st health coaching call
		X					1 st Health Coaching Call; review Fitabase before call; record notes on MI Visual Aids;
		X					2 nd Health Coaching Call; review Fitabase before call; record notes on MI Visual Aids;
\$					X		Mail MI Visual Aids (calls 3-5)
		X					3 rd Health Coaching Call; review Fitabase before call; record notes on MI Visual Aids;
		X					4 th Health Coaching Call; review Fitabase before call; record notes on MI Visual Aids;
		X					5 th Health Coaching Call; review Fitabase before call; record notes on MI Visual Aids; Schedule 13-week Assessment 
 Schedule remote assessment w/ [name] via MYHealth calendar Ask survey preference (mail/online) (see Assessment Call 1 Script ...)
		X					Waitlist Control Group – 13-week Assessment: 
 Schedule remote assessment w/ [name] via MYHealth calendar Ask survey preference (mail/online) Inform ppt Fitbit will be mailed (see Assessment Call 1 Script ...)
				(X)		X	Survey packet & cover letter mailed to ppt (optional: email w/ REDCap link)
							Verify receipt of packet (see Assessment Call 2 Script ...)
		X		X			Reminder to ppt about assessment (need another person present for physical function tests) (see Assessment Call 3 Script ...)

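### At week 13 only immediate-arm participants can be supported through their assessments by the person who coached them, because the plan does not separate coaching from assessment staff

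*Combined protocol and SAP*

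**What the plan says.** All the relevant text is in Section 9.0.

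- **Health Coach Calls / MI.** "Research assistants will undergo MI training specific to this study", so the coaches are research assistants. The paragraph adds: "The health coach also provides tech support to the participant for assessments (activPAL and performance testing", together with help in "using Fitbit with their mobile app (weeks 1, 2, 13, & 26". There are five coaching calls, in weeks 3, 5, 7, 9 and 11.
- **Follow-up assessment.** On who is sent the monitor, the plan states: "The ActivPAL3™ monitor, and instructions will be mailed to all participants to collect 1-week of data for secondary outcomes during week 13". Questionnaires go out in the same mailing. Then: "The RA will call to review the instructions and answer any questions". For week 26: "The same procedure will be used for the 3-month post-intervention follow-up assessment".
- **Study Flow table.** In the immediate arm the fifth coaching call also schedules the week-13 assessment. Waitlist controls get a separate scheduling call with the same script. The row "Follow-up for incomplete surveys; return of activPAL (see Assessment Call 4 Script" appears twice, once before randomization and once at week 13. Neither row says who calls.
- **Remote assessment of physical performance.** The investigator runs the chair stand and balance tests by videoconference, in both arms.
- **Waitlist Control.** Controls keep their usual lifestyle for 12 weeks and then receive the full coached program.

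No section says that the person supporting an assessment must be someone other than the participant's coach, and none describes masking of the staff who handle assessments.

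**The concern.** When the week-13 measurements are taken, the two arms differ in more than the intervention's true effect. One arm may be helped by a person who spent five calls building rapport and motivation. The other can only be helped by someone who has never coached them.

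The outcomes most exposed are those that respond to effort or to being watched by someone who cares about the result:

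- **Chair stand.** "The participant is instructed to perform the test quickly, but safely", so the count depends on how hard the participant tries.
- **activPAL week.** The coach helps set, and then tracks, goals for daily steps and active hours. Table 2 counts daily steps and waking hours with at least 250 steps among the activPAL measures. The person who set the targets may therefore support the week in which they are measured.
- **Ratings of the coach and program.** Table 2 includes a scale on the health coach's support for autonomy, and program satisfaction is a primary process measure. A participant could be prompted to finish these ratings by the person being rated.

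Masked scoring of the recordings would not remove this, because it would act on the participant's effort and answers and not on the scorer.

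**Working it through.** **1. Do the listed weeks cover the assessments?** The week list follows the mention of the Fitbit, so it could be read as applying to the Fitbit alone. It includes week 1, when no Fitbit is yet in use, and weeks 1, 13 and 26 are exactly the assessment weeks. The list therefore covers assessment support.

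**2. Who has been coached at each assessment?**

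| Assessment | Immediate arm | Waitlist arm | Could the helper be the participant's own coach? |
|---|---|---|---|
| Week 1 | no calls yet | no calls yet | neither arm |
| Week 13 | five calls, the last in week 11 | no calls | immediate arm only |
| Week 26 | no study contact in weeks 14–25 (Table 3) | full program since week 13 | both arms, controls more recently |

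The imbalance is in the prior relationship, and it is one-sided only at week 13.

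**3. The plan's own figure.** Inputs from Section 10.0, Power / Sample Size Calculation: 25 per arm, difference 8.1, SD 10, two-sided 5%.
- Standardized difference = 8.1/10 = 0.81.
- Standard error = sqrt(2/25) = 0.283 SD.
- Power by the noncentral t distribution = 80.1%, against the stated 80%.
- Attrition: 25/0.80 = 31.25, rounded up to 32 per arm, as stated.

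The design reproduces, and nothing in it measures this bias.

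**4. Illustration with an assumed bias.** The documents give no size. Suppose coach involvement shifts the immediate arm by 0.1 or 0.2 SD at week 13 and there is no true effect.

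| Assumed shift | In standard errors | Rejection rate, normal | Rejection rate, t-test |
|---|---|---|---|
| 0.1 SD | 0.1/0.283 = 0.354 | 6.4% | 6.4% |
| 0.2 SD | 0.2/0.283 = 0.707 | 10.9% | 10.7% |

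This is the simple two-sample comparison. Adjusting for baseline would reduce the standard error but not the shift.

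**5. Effect on the estimate.** The proportional overstatement depends on the true effect, which is also an assumption.
- True 0.5 SD with a 0.1 shift: 0.1/0.5 = 20%.
- True 0.3 SD with a 0.2 shift: 0.2/0.3 = 67%.
- Planned 0.81 SD: 0.1/0.81 = 12% to 0.2/0.81 = 25%.

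Required sample size goes as 1 over the squared effect. Reading 0.5 as 0.6 would make a later trial 1 − (0.5/0.6)² = 31% too small. Reading 0.3 as 0.5 would make it 1 − (0.3/0.5)² = 64% too small. This applies only if the later trial is sized on an affected outcome.

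**The case against.** The strongest case on the other side has five parts.

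- **Support is available to both arms.** A reader might infer that controls go without help. The text does not say so: the coach paragraph has no arm restriction and includes a week before randomization, and the follow-up packet goes to everyone. This stands. What differs at week 13 is the relationship, not the presence of help.
- **The coach does not run the tests.** The investigator reviews the instructions and signals start and stop, and participants also have print and video instructions. The coach's stated role is technical. This stands, and it limits the plausible size of any effect, but it does not remove the contact around the test or during the activPAL week.
- **Self-reported physical function is barely touched.** Questionnaires come by mail or online, and the named coach support covers only activPAL and performance testing. The only links are the call about the packet and an unassigned follow-up of incomplete surveys. An unmasked waitlist design carries self-report bias whoever helps. This largely stands, so the point should not be read as showing that the primary efficacy outcome is biased.
- **Week 26.** A reader might carry the same one-sided bias forward. The documents do not support that, because controls have by then been coached, and more recently.
- **Familiarity helps retention.** Retaining 80% is a feasibility target, and a known helper may serve it. This is a real cost, to be weighed against the gain.

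What remains is that nothing prevents the coach from supporting the week-13 assessment of a participant he or she coached, and this can happen in one arm only.

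**Conclusion.** The concern holds in a limited form. The plan lets one person both coach a participant and support that participant's follow-up assessments, and at week 13 this is possible only in the immediate arm. The chair stand and the activPAL measures are the outcomes at risk, followed by ratings of the coach and program. Any effect on self-reported physical function is less direct, and at week 26 the direction is uncertain.

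The size is unknown. The 6.4% to 10.9% range rests entirely on an assumed shift of 0.1 to 0.2 SD and 25 analysed per arm. It shows what such a shift would do and is not an estimate of the bias. The conclusion also assumes that coaches would in practice support their own participants, which the text permits but does not require.

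This does not undermine the feasibility aims. It is worth correcting because Section 10.0 uses the results to inform the effect size and sample size of a larger trial, and the correction is cheap.

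**What to change.** In Section 9.0, amend the Health Coach Calls / MI and Follow-up assessment paragraphs to state that at week 13 and, for consistency, at week 26, in both arms, a research assistant who has not coached that participant will:

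- make the assessment calls, using the existing scripts;
- give technical support for the activPAL and the video tests;
- follow up any incomplete surveys.

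Limit the coach's own technical support to setting up and using the Fitbit. Simple scheduling of the week-13 visit may stay in the fifth coaching call. Name the responsible role in the matching rows of the Study Flow table.

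**Cost.** A few wording changes and a rota in which coaches cover each other's participants. The Intervention Fidelity paragraph refers to coaches in the plural, so no new post should be needed, although their number is not stated. Participants will have a less familiar helper around the follow-up assessments. The rota will be tightest for Spanish-speaking participants, because Section 24.0 relies on bilingual team members and does not say how many there are. If a swap is impossible for a participant, record it so that its frequency by arm can be reported.
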